2. HIPOTESIS:

Intermittent suction improves the diagnostic yield of pancreatic lesions compared to standard (continuous) suction. Up to our knowledge this method has not been yet evaluated.

3. STUDY DESIGN:

Interventional study with diagnostic purpose, longitudinal, prospective, unicentric, blinded for participant and anatomopathologist, in patients with solid pancreatic lesions with indication of cytological sampling by Endoscopic Ultrasound referred to the Endoscopy Unit of Hospital Universitario de la Princesa from January 2019 to December 2019.

Following clinical practice, an endoscopic ultrasound fine-needle aspiration (EUS-FNA) with a 25 gauge needle will be performed to each participant. The patients will be divided into two arms with a 1:1 ratio:

- a) Intermittent aspiration: Intervention arm. Endoscopic ultrasound will be done for the localization of the lesion and to localize the site of puncture. Prior to the puncture of the lesion the stylet is removed and a vacuum syringe is prepared with 10 cc of vacuum allowing the generation of continuous pressure inside and connected to the end of the needle. Once the lesion is punctured 15 movements in and out of the lesions will be made while the syringe is opened and closed on and off for a total of 3 times each pass. A total of 4 passes will be done in each lesion.
- b) Continuous/standard aspiration: Same procedure but once the lesion is punctured 15 movements in and out of the lesions will be made while the syringe remains opened.

Randomization will be done with the generation of a computer-generated random list using Epidat 4.0. software (SERGAS®, Santiago de Compostela, Spain).

The endoscopic ultrasound will be done with an Olympus linear echoendoscope (GF-UTC 260 Olympus® Tokyo, Japan) under Propofol sedation by an Anesthesiologist.

Each pass will be sent to the pathologist separately to evaluate their individual characteristics and to determine which one is diagnostic. A complete report will be done assessing:

- a) Cellularity
- b) Hematic contamination
- c) Presence of cell block and possibility of doing immunohistochemistry

4. OUTCOME MEASURES:

- a. Primary outcome measure: Increase in diagnostic yield of pancreatic solid lesions
- b. Secondary outcomes:
 - Sample Celularity: Number of malignant cluster of cells on each endoscopic pass
 - Blood contamination: Percentage of blood contamination of the slides
 - Number of passes to reach a positive cytological diagnosis

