5. ELEGIBILITY CRITERIA:

- a) Inclusion Criteria:
 - Pancreatic solid lesion
 - Patients over 18 years old
 - Suitable for endoscopy
- b) Exclusion Criteria:
 - Contraindication for endoscopy
 - Active anticoagulant therapy
 - Thrombocytopenia or coagulopathy in the absence of its correction prior to the procedure
 - Absence of informed consent
 - Pregnancy
 - Not accessible lesion for endoscopic ultrasound puncture

6. STATISTICAL ANALYSIS PLAN:

Data will be expressed as means and standard deviation for quantitative variables or frequencies and percentages for the categorical ones. Variables with non-normal distributions will be represented as means and percentage ranges.

Randomization will be done with a computer-generated random list in a 1: 1 ratio. The chi-square test will be used to compare qualitative variables. Correlation kappa values will be offered between both methods. In order to evaluate the differences in diagnostic yield, the sensitivity after the completion of each pass will be calculated by correlating the continuous values of confusion with the final cytology with the Spearman test. The number of optimal passes depending on the method will be calculated by maximizing that the following passes would not modify the additional diagnostic yield more than 10% over the accumulated one. On the other hand, the cellularity and blood contamination graduated in its three levels will be contrasted between both methods with an analysis of McNemar. All the variables that could potentially modify the diagnostic yield of both methods will be compared with univariate and later multivariate analysis by means of logistic regression analysis with the STATA application (v13.0, StataCorp, College Station, Texas, USA). The protocol will be approved by the Ethical Committee of the Hospital Universitario de la Princesa before the start of the study.

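### The secondary outcome counting passes to a positive diagnosis has no value for patients never positive in the 4 passes, so a mean-based comparison covers only successes and can mislead

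*Combined protocol and SAP*

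**What the plan says.** Section 4 gives the secondary outcome as "Number of passes to reach a positive cytological diagnosis". Section 3 states, under the intermittent arm, "A total of 4 passes will be done in each lesion". The continuous arm is described as the same procedure apart from syringe handling, so the limit of 4 applies to both. Passes are read one by one: "Each pass will be sent to the pathologist separately to evaluate their individual characteristics and to determine which one is diagnostic".

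Section 6 assigns no test to this outcome and says nothing of patients without a positive pass. Three of its general rules could reach it:

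- "Data will be expressed as means and standard deviation for quantitative variables";
- for non-normal variables, a mean with a percentage range;
- for categorical variables, frequencies with a chi-square test.

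Two further analyses touch on passes. One is per-pass sensitivity: "the sensitivity after the completion of each pass will be calculated by correlating the continuous values of confusion with the final cytology". The other is a stopping point for each technique: "The number of optimal passes depending on the method will be calculated" so that later passes "would not modify the additional diagnostic yield more than 10% over the accumulated one".

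The introduction says that solid lesions may be non-neoplastic, and section 5 admits any solid lesion. The plan does not say whether a specific benign diagnosis counts as positive.

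**The concern.** The outcome is a count from 1 to 4 that does not exist for a patient who is never positive. The trial's hypothesis is that yield differs by technique, so the number of patients without a value should differ by arm. A mean drops them, and what remains is a comparison of two groups formed by the result of treatment, not by randomisation.

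Two things follow. First, extra diagnoses made late or in difficult lesions add high counts to the better arm's mean, while the other arm's failures disappear. The secondary outcome could then appear to contradict the primary one. Second, even where the order comes out right, the extra patients diagnosed are not credited, and most of the power is lost.

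**Working it through.** **Inputs.** The documents give no sample size, yield or effect, so there is no figure to reproduce. Only the limit of 4 passes and the 1:1 allocation come from the plan. Assumed: 30 per arm and final yield 74% (comparator) against 90%.

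**Formula.** With f_k the probability of a first positive at pass k, yield = Σf_k and the mean among successes = Σk·f_k / Σf_k.

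**By hand.** Curves are cumulative percentages after passes 1/2/3/4.

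- Comparator 60/70/72/74: (0.60·1 + 0.10·2 + 0.02·3 + 0.02·4)/0.74 = 0.94/0.74 = 1.270.
- Higher-yield arm with a late gain, 60/70/80/90: (0.60 + 0.20 + 0.30 + 0.40)/0.90 = 1.50/0.90 = 1.667. It diagnoses 16 points more patients but looks slower.
- Same arm against a comparator that rises more steadily, 45/60/69/74: (0.45 + 0.30 + 0.27 + 0.20)/0.74 = 1.22/0.74 = 1.649. The two means are now nearly equal.
- Early gain, 80/86/88/90: (0.80 + 0.12 + 0.06 + 0.08)/0.90 = 1.06/0.90 = 1.178. This is below both comparators, so the expected order is right.

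**Simulation.** At least 100,000 trials per cell. Entries are the percentage of trials in which the higher-yield arm has the larger mean among successes. The proportional curve is 60/70/72/74 multiplied by 90/74.

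| Comparator | 60/70/80/90 | 65/77/84/90 | 70/80/85/90 | 75/82/86/90 | Proportional | 80/86/88/90 |
|---|---|---|---|---|---|---|
| 60/70/72/74 | 95 | 84 | 71 | 56 | 50 | 30 |
| 55/66/71/74 | 84 | 64 | 47 | 32 | 26 | 13 |
| 50/62/69/74 | 65 | 40 | 26 | 15 | 11 | 4 |
| 45/60/69/74 | 52 | 27 | 15 | 8 | 5 | 2 |

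An all-patient log-rank points the wrong way in 14/10/7/5/6/4% across the first row, and in 1-14% over the whole table.

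**Gain only in difficult lesions.** Take 60% easy lesions (0.90 per pass in both arms) and 40% difficult (0.10 against 0.30 per pass).

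- Yield: 0.6·(1 − 0.1⁴) + 0.4·(1 − 0.9⁴) = 74%, against 0.6·(1 − 0.1⁴) + 0.4·(1 − 0.7⁴) = 90%.
- Mean among successes: 1.35 against 1.43, so reversed.
- Wrong order: 65% of trials, against 7% for log-rank.

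A milder setting (50% easy, difficult 0.165 against 0.33) gives 51% and 9%.

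**Same odds ratio at every pass.** With lesion difficulty varying from none to very large:

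- wrong order among successes 16-20% (21-24% at 20 per arm, 10-14% at 50), against 3% for log-rank;
- power in the right direction 10-15% for a t-test among successes, against 45-49% for log-rank.

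**Do the two planned analyses fill the gap?**

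- *10% rule.* It gives one number per technique and marks where the curve flattens, not how many patients are diagnosed. If all later passes together may add at most 10% of the accumulated yield, the comparator 60/70/72/74 needs 2 (74/70 = +5.7%) and the six curves need 4/3/3/2/2/2. If only the next pass is judged, they need 4/2/2/1/2/1 against 2.
- *Per-pass sensitivity.* Its reference, the final cytology, is undefined. Against an independent final diagnosis it would show accumulated yield. Against the pooled result of the same 4 passes, never-positive patients drop out again: 70/80/85/90 becomes 78/89/94/100% (70/90, 80/90, 85/90), which looks worse than the comparator's 81/95/97/100% (60/74, 70/74, 72/74).

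**The case against.** The strongest reply is that the plan never says the mean will be taken among successes. The result could be treated as five categories (pass 1, 2, 3, 4, none) under section 6's rule for categorical variables, which keeps every patient. This stands as a possible reading, but the plan does not state it. The two mean-based rules apply at least as naturally to a count, and neither can hold a patient without a value.

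A second reply is that the large reversal figures rest on a comparator that is nearly flat after pass 2. This also stands. The first row of the table cannot be taken as typical: with 45/60/69/74 most patterns rank correctly most of the time.

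A third is that section 6 already looks at accumulated yield by pass. That is partly true, but neither analysis is assigned to this outcome or compares it between arms, and what each shows depends on an unstated reading.

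A reader might infer that the plan commits itself to a successes-only mean, or that this outcome will rank the better technique worse. The documents support neither. The first is an inference from general rules. The second depends on yields and curve shapes that the documents do not give, and it does not hold for clearly early or uniform gains.

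**Conclusion.** The outcome is undefined for never-positive patients, and no denominator or test is named. That much rests on the text alone. If it is summarised by a mean, the comparison is among patients selected after randomisation. Under the assumed yields, the risk of a wrong order runs from about 2% to 95%, because it is driven by when each arm's diagnoses occur. When the technique helps equally at every pass, the order is usually right and the main cost is power.

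The primary comparison of yield is not affected. For one secondary outcome of a pilot this is a point to consider, not a critical defect.

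**What to change.** Add to section 6:

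- Analyse all randomised patients who undergo puncture, and report by arm how many were randomised but not punctured.
- Show the cumulative proportion with a positive diagnosis after each pass, by arm. Censor never-positive patients after pass 4, and compare arms by log-rank or discrete-time logistic regression.
- State in advance whether a specific benign diagnosis counts as positive. That choice is the investigators'. If it does not count, add a supplementary analysis in lesions finally judged neoplastic.
- Keep per-pass sensitivity and the 10% rule as descriptive results.

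The cost is wording only: each pass is already read separately, so no new data are needed. There is one small downside. Lesions that can never be positive dilute the all-patient comparison. For 70/80/85/90 against 60/70/72/74, with 10/20/30% such lesions, log-rank power falls from 30% to 22/17/13% and wrong order rises from 7% to 12/16/20%. The mean among successes stays wrong in 68-70% of trials in the same settings.

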**INTERMITTENT VERSUS CONTINUOUS SUCTION TECHNIQUE IN THE DIAGNOSIS OF
PANCREATIC SOLID LESIONS. A PILOT STUDY**

STUDY PROTOCOL 03/02/2019

NCT03829748

PRINCIPAL INVESTIGATOR

Dra. [name]

SUB-INVESTIGATORS

[name] [name]

[name] [name]

Gastroenterology Department, Endoscopy Unit

Hospital Universitario de la Princesa

Madrid, Spain

1. INTRODUCTION:

Solid lesions of the pancreas can be neoplastic or non neoplastic and it is important to accurately differentiate between them because of the poor prognosis related to pancreatic neoplasm. There are many types of solid pancreatic lesions: pancreatic adenocarcinoma, neuroendocrine tumor, lymphoma, solid pseudopapillary neoplasm and pancreatic metastasis.

There are several diagnostic methods for the study of pancreatic solid lesions. The different imaging test allow detection and characterization of those lesions, but most times an anatomopathological diagnosis is needed before establishing the most appropriate treatment.

Endoscopic Ultrasound guided fine needle aspiration (EUS-FNA) is the diagnostic method of choice for the diagnosis of these lesions as it detects small lesions that sometimes cannot be found in radiological imaging test, evaluates vascular invasion and the presence of liver metastasis, and allows pancreatic puncture for a cytological diagnosis. EUS-FNA is the safest technique for pancreatic puncture and the least related to needle track seeding.

In order to gather as much material as possible different techniques have been proposed:

- Fanning technique and multiple pass technique: to guide the needle into different regions of the target lesions with or without removing the needle out of the lesion depending on whether the lesion is hard or soft.
- Use of stylet: there are no data clearly demonstrating that the use of suction increases the yield of EUS-FNA. Some authors do slow withdrawal of the stylet.
- Size of the needle: 19 gauge, 22 gauge, 25 gauge, depending on the localization, size and vascularization. There is increasing evidence that smaller needles offer at least similar results in diagnostic yield compared to larger needles and are also easier to manipulate.
- Use of suction: there is conflicting evidence in this point. Several studies have evaluated the use of high volume aspiration vs low volume aspiration, continuous aspiration vs no aspiration and suction with empty syringe vs water-filled syringe but none is clearly better than other.

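### The one analysis the SAP ties to differences in diagnostic yield measures sensitivity against an undefined final cytology; if that means the four pooled passes, both arms reach 100% after pass 4 whatever the true difference

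*Combined protocol and SAP*

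**What the plan says.** Section 4 gives the outcome as "Primary outcome measure: Increase in diagnostic yield of pancreatic solid lesions", with no operational definition of yield.

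Section 6 introduces one analysis with the words "In order to evaluate the differences in diagnostic yield". In it, "the sensitivity after the completion of each pass will be calculated by correlating the continuous values of confusion with the final cytology", using the Spearman test. The term final cytology occurs only there and is not defined. No surgical pathology, later tissue, follow-up or composite reference is named in any section.

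The only cytology described is in section 3: "A total of 4 passes will be done in each lesion", and "Each pass will be sent to the pathologist separately to evaluate their individual characteristics and to determine which one is diagnostic". The continuous arm follows the same procedure, and patients are allocated 1:1 to parallel arms.

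Two other sentences in section 6 could bear on yield. One is general: "The chi-square test will be used to compare qualitative variables". The other describes a logistic regression: "All the variables that could potentially modify the diagnostic yield of both methods will be compared with univariate and later multivariate analysis". Neither is assigned to the between-arm comparison of the primary outcome.

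**The concern.** Sensitivity needs a reference that can identify lesions the test missed. If the reference is the test's own pooled result, a malignant lesion that is negative on all four passes is not reference-positive and is not counted. Those are the failures that a better suction technique should reduce.

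Because the arms are parallel, each would have its own reference. The arm that misses more lesions is divided by a smaller number, which raises its apparent sensitivity. The hypothesis in section 2 is that intermittent suction improves yield. The analysis named for that question could show nothing after the full four passes and give a misleading contrast before then.

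**Working it through.** **Inputs.** From the documents: four passes per lesion, each read separately; sensitivity calculated after each pass; parallel 1:1 arms. The documents give no yield, sample size or expected difference, so there is no figure to reproduce and every rate below is an assumption. Sensitivity is taken in its ordinary 2x2 sense, with no false positives. *After each pass* is read as cumulative, which fits the same section's rule for the optimal number of passes, based on accumulated yield.

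**Formula.** Let c_k be the true cumulative sensitivity after pass k, meaning the share of malignant lesions positive on at least one of passes 1 to k. If the reference is positive when any of the four passes is positive, then

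apparent sensitivity after pass k = c_k / c_4.

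At k = 4 this is c_4 / c_4 = 1 in any arm with at least one positive lesion.

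**Constant per-pass detection p**, independent passes: c_k = 1 − (1 − p)^k.

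- p = 0.50: c = 50.0 / 75.0 / 87.5 / 93.8%. Divided by 93.75%: 53.3 / 80.0 / 93.3 / 100%.
- p = 0.35: c = 35.0 / 57.7 / 72.5 / 82.1%. Divided by 82.1%: 42.6 / 70.3 / 88.3 / 100%.

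Differences in percentage points, intermittent minus continuous, after passes 1 / 2 / 3 / 4:

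| Assumed p | True difference | Apparent difference |
|---|---|---|
| 0.50 vs 0.35 | 15.0 / 17.3 / 15.0 / 11.6 | 10.7 / 9.7 / 5.0 / 0 |
| 0.50 vs 0.40 | 10.0 / 11.0 / 9.1 / 6.7 | 7.4 / 6.5 / 3.3 / 0 |
| 0.50 vs 0.30 | 20.0 / 24.0 / 21.8 / 17.8 | 13.9 / 12.9 / 6.9 / 0 |
| 0.70 vs 0.60 | 10.0 / 7.0 / 3.7 / 1.75 | 9.0 / 5.5 / 2.0 / 0 |

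A simulation of 200,000 lesions at each of p = 0.30 and p = 0.50 agreed with the formula.

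**Other curve shapes** (cumulative sensitivities chosen for illustration; continuous arm 50/62/70/75%, which divided by 75 gives 66.7/82.7/93.3/100%):

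- Intermittent 60/75/84/90%, divided by 90, gives 66.7/83.3/93.3/100%. True +10/+13/+14/+15 becomes 0/+0.7/0/0.
- Intermittent 55/68/80/90%, divided by 90, gives 61.1/75.6/88.9/100%. True +5/+6/+10/+15 becomes −5.6/−7.1/−4.4/0.

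**Arms differing only in the share of lesions that can ever be diagnosed** (70% vs 90%, per-pass detection 0.6 in those): c_4 = 0.70 × 0.9744 = 68.2% and 0.90 × 0.9744 = 87.7%. The true difference is 19.5 points. The share cancels from c_k / c_4, so the apparent difference is 0 after every pass.

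**Taking the Spearman wording literally.** For two yes/no variables the Spearman coefficient equals phi. Since a positive by pass k implies a positive by pass 4, phi = √[c_k(1 − c_4) / (c_4(1 − c_k))], which is again 1 at pass 4. For p = 0.50 it is 0.26 / 0.45 / 0.68 at passes 1 to 3, and for p = 0.30 it is 0.37 / 0.57 / 0.78. The better arm scores lower.

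**The case against.** The 100% result depends on how three things are read: final cytology as the pooled passes, *after each pass* as cumulative, and sensitivity in the 2x2 sense. The first is not settled by the text. If an independent final diagnosis was meant, the distortion disappears. That stands, and it is why the conclusion is conditional. On the second, pass 4 taken alone would not give 100% (about 40% and 53% for p = 0.30 and 0.50), but the reference to accumulated yield favours the cumulative reading. On the third, the literal Spearman version fares no better.

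The sentence could also be about gain from pass to pass rather than a contrast between arms, since the next one sets the optimal number of passes. But the hypothesis concerns the arms, and this is the only analysis introduced for differences in yield.

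A raw-yield comparison is available: each pass is classed as diagnostic or not, and the chi-square or logistic regression could use that without any reference standard. This is the strongest point, but the SAP does not name either as the primary comparison.

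Finally, the vanishing and reversing curves were chosen by hand, and under constant per-pass detection the apparent sensitivity difference at passes 1 to 3 keeps its sign. They show what can happen, not what is likely. Pilot status does not help: the study is randomised and states a directional hypothesis.

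**Conclusion.** The point holds. The plan evaluates differences in its primary outcome through a sensitivity whose reference is undefined, and the only cytology it describes is the test under study. If final cytology is the pooled four passes and sensitivity is cumulative, the apparent difference after pass 4 is exactly 0. Under the constant per-pass rates assumed here it would hide true differences of 1.75 to 17.8 points, and 15 points in the two illustrative curves. The pass-4 result is algebra and does not depend on the rates. The size and direction of the distortion at passes 1 to 3 do depend on them. Even if an independent reference was intended, the plan does not name it. This should be corrected before the arms are compared.

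**What to change.** **Primary analysis.** Use the cumulative proportion of all randomised patients in each arm with a diagnostic result after each pass. Compare the arms at one named pass, for example after pass 4, by chi-square or a risk difference with a 95% confidence interval. State what counts as diagnostic, including whether a specific benign diagnosis does, since the Introduction notes that "Solid lesions of the pancreas can be neoplastic or non neoplastic". Count non-diagnostic samples, and randomised patients without a sample, as failures. This uses data already planned and costs only wording, but the definition must be agreed before the arms are compared.

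**Sensitivity, if also reported.** Define the reference from outside the study passes: surgical pathology, later tissue, or the clinical and imaging course in routine records at a time fixed in the SAP, classified without knowledge of arm. Count four-pass negatives that prove malignant as false negatives, and report unverified cases by arm. The protocol describes no follow-up, so this needs a later record review. It would delay the sensitivity result, and some unresected negatives would remain unverified. The primary analysis above does not depend on it.

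### Section 6 plans no between-arm yield comparison using all four separately read passes per patient, and its Spearman step does not compare the arms

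*Combined protocol and SAP*

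**What the plan says.** Section 4 gives as "Primary outcome measure: Increase in diagnostic yield of pancreatic solid lesions", without stating the unit (lesion or pass), the pass count or the test.

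Section 3 sets the data structure. In the intervention arm, "A total of 4 passes will be done in each lesion". The control arm is described as "Same procedure but once the lesion is punctured 15 movements in and out of the lesions will be made while the syringe remains opened", which I read as four passes there too. No stop at the first positive pass is mentioned. The passes are not pooled before reading: "Each pass will be sent to the pathologist separately to evaluate their individual characteristics and to determine which one is diagnostic". Each patient therefore supplies four yes/no yield results.

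On yield differences, section 6 says that "the sensitivity after the completion of each pass will be calculated", and it ties this to a Spearman correlation between pass-level values and the final cytology. The next rule, for the optimal number of passes, works on a cumulative scale: "the following passes would not modify the additional diagnostic yield more than 10% over the accumulated one".

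Other items touch on yield or passes. "Number of passes to reach a positive cytological diagnosis" is a secondary outcome with no named test. Cellularity is recorded on each pass. Section 6 also names chi-square for qualitative variables in general, and univariate then multivariate logistic regression.

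**The concern.** The hypothesis in section 2 is that one suction technique gives better yield than the other. If the technique makes each pass better, the evidence is spread over all four passes. A cumulative look reduces those results to a single yes/no per patient: was anything positive so far? After several passes most lesions may be positive in both arms, so a per-pass advantage is compressed. The look after pass 1 is not compressed, but it uses one result of four.

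The stated step has a more basic problem. A correlation between pass results and final cytology describes agreement within a set of patients; it does not estimate a difference between arms. As written, the between-arm test of the primary outcome is left to inference. A single-centre, one-year pilot has little information to spare, and the four readings will already be in the database.

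**Working it through.** **No figure to reproduce.** The documents give no sample size, alpha, power, expected yield or within-patient correlation. Everything below is an assumption except the four passes and the 1:1 ratio.

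**Assumptions.** n = 30 per arm; probability p that a pass is diagnostic, 0.55 versus 0.70; two-sided 5%; correlation ρ between passes in a patient (beta-binomial model), from 0 to 0.8.

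**Step 1: cumulative yield.** With M = (1−ρ)/ρ and b = (1−p)M, the chance that four passes are all negative is the product of (b+j)/(M+j) for j = 0 to 3. At ρ = 0.2, M = 4:
- p = 0.55, b = 1.8: (1.8/4)(2.8/5)(3.8/6)(4.8/7) = 0.109, so yield is 0.891.
- p = 0.70, b = 1.2: (1.2/4)(2.2/5)(3.2/6)(4.2/7) = 0.042, so yield is 0.958.

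A 15-point difference per pass becomes 6.7 points after pass 4.

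**Step 2: signal to noise at ρ = 0.2.**
- After pass 4: SE = √[(0.891×0.109 + 0.958×0.042)/30] = 0.068; 0.067/0.068 = 0.99.
- Pass 1: SE = √[(0.55×0.45 + 0.70×0.30)/30] = √(0.4575/30) = 0.1235; 0.15/0.1235 = 1.21.
- All four passes, patient as unit: SE = √[0.4575×(1+3ρ)/(4×30)] = √(0.4575×1.6/120) = 0.078; 0.15/0.078 = 1.92.

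The normal approximation, power ≈ Φ(ratio − 1.96), gives about 17%, 23% and 48%.

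**Step 3: simulation.** I ran 20,000 trials per row, using Pearson chi-square for cumulative yield and a Welch t-test on each patient's fraction of diagnostic passes:

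| ρ | After pass 4 | Pass 1 | All four passes |
|---|---|---|---|
| 0 | 3% | 22% | 66% |
| 0.2 | 16% | 22% | 47% |
| 0.4 | 19% | 22% | 37% |
| 0.6 | 19% | 22% | 30% |
| 0.8 | 21% | 22% | 26% |

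Independent runs agree to about one percentage point. Type I error of the all-passes test was about 5%. It beat the looks after passes 1, 2, 3 and 4 in every row.

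**Step 4: other rates.** With 60% versus 75% per pass and 80% power, n per arm at ρ = 0 / 0.2 / 0.4 / 0.6 / 0.8 is:
- after pass 4: 484 / 286 / 229 / 197 / 173;
- pass 1: 152 throughout;
- all four passes, 152×(1+3ρ)/4: 38 / 61 / 84 / 106 / 129.

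Relative to the all-passes analysis, the look after pass 4 keeps 38/484 = 8%, then 21%, 37%, 54% and 129/173 = 75% of the information. Pass 1 keeps 25% to 85%.

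**Step 5: do the other planned items fill the gap?**
- Passes to diagnosis ignores every pass after the first positive. Given a log-rank test, it reaches about 28% at ρ = 0.2 in the Step 3 setting, against 47%.
- Logistic regression with one row per patient is the cumulative outcome again. With one row per pass and no clustering, it treats correlated passes as independent.
- Cellularity is not yield, and the optimal-pass rule does not test the arms.

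**Step 6: where the ordering reverses.** Suppose the technique only makes more lesions reachable (75% versus 92%), with the same per-pass rate in reachable lesions. Any-of-four yield then has about 44% power and the all-passes test 33%. In my check the direction was the same for per-pass rates of 0.6 to 0.9 within reachable lesions.

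**The case against.** The strongest objection concerns the question being asked. The hypothesis speaks of the yield of pancreatic lesions, naturally read per lesion. If four passes give nearly the same yield in both arms, that may be the true answer, and a per-pass test answers a different question. This stands. It is why the per-pass comparison belongs beside the per-lesion one and should not reduce it to description.

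Second, the chi-square benchmark is mine. Section 6 names chi-square only in general and attaches Spearman to yield, so the power figures describe a plausible repair of the plan, not its stated analysis. This also stands. It strengthens the case for writing down a between-arm test.

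Third, a reader might infer several stronger claims that the documents do not support:
- That yield is examined only through cumulative looks. Passes to diagnosis, per-pass cellularity and logistic regression are also planned, though under-specified.
- That the plan discards most of the information. This depends on unstated rates and correlation. With 60% versus 75% it is true of the look after pass 4 at ρ up to 0.4 but not at 0.6, and of pass 1 only below about 0.33.
- That the ceiling undermines the whole yield analysis. Later passes cannot raise sensitivity after pass 1.
- That the trial would miss a difference the better test would find. With 30 per arm and correlated passes, the better test also has under 50% power.

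Nothing is lost for good either, because every pass is read and recorded.

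**Conclusion.** The point holds in a limited form. Section 6 specifies no between-arm comparison that uses all four pass results with the patient as the unit, and the Spearman step it attaches to yield does not compare the arms. Under the 30-per-arm assumptions, the all-passes comparison raises power from about 15–22% to 47% at correlation 0.2, but only from 21–22% to about 26% at 0.8. The direction held for all the per-pass rates and correlations tried; the size rests on figures the documents do not give. It reverses if the benefit is confined to otherwise unreachable lesions. The change should be made because it is cheap and the data will exist. The number of passes is not at issue.

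**What to change.** Replace the Spearman step in section 6 with two pre-specified between-arm comparisons:

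1. **Yield per lesion** at one named pass count, as a difference in proportions with 95% CI. Define what counts as diagnostic and, if sensitivity is meant, the reference diagnosis and denominator.
2. **Yield per pass**, using all four results with the patient as the unit: a t-test on each patient's fraction of diagnostic passes, or a logistic GEE clustered on patient with arm and pass number. Report the per-pass difference with 95% CI, and label it as yield per pass.

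Keep cumulative yield by pass beside the second comparison. State its limitation: it is weaker than four-pass yield if the technique helps only with otherwise unreachable lesions. State which comparison is primary before the results are seen.

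The cost is a paragraph in section 6 and a few lines of Stata. There are no new data and no change to the procedure.
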